11.2.8.4 Time to Clinical Maturation

Time to clinical maturation is defined as the number of days from baseline procedure to date of clinical maturation (first date of 4-week window with 75% successful 2 needle cannulation).

Clinical maturation is defined as 75% of dialysis sessions with 2 needle cannulation for 4 weeks.

11.2.8.5 Radiographic Maturation Success Rate

Radiographic maturation success rate is defined as the percentage of subjects that achieve radiographic maturation by end of study.

Radiographic maturation is defined as fistula diameter \geq 5mm, fistula flow \geq 500 mL/min as assessed by physician based on ultrasound imaging and adjudicated by CEC.

11.2.8.6 Clinical Maturation Success Rate

Clinical maturation success rate is defined as the percentage of subjects that achieve clinical maturation by end of study.

Clinical maturation is defined as 75% of dialysis sessions with 2 needle cannulation for 4 weeks.

11.2.8.7 6-Month Patency Rate

6-month patency rate is defined as the percentage of subjects that have patent access at 6 months if both radiographic and clinical maturation definitions have been met.

6-month patency rate as defined by the status (yes/no) of an arteriovenous dialysis access with detectable blood flow through and beyond the anastomosis shown by either an imaging modality or physical examination (presence of a palpable thrill or audible bruit along some point of the arteriovenous dialysis access beyond the arteriovenous anastomosis).

11.2.8.8 12-Month Patency Rate

12-month patency rate is defined as the percentage of subjects that have patent access at 12 months if both radiographic and clinical maturation definitions have been met.

12-month patency rate as defined by the status (yes/no) of an arteriovenous dialysis access with detectable blood flow through and beyond the anastomosis shown by either an imaging modality or physical examination (presence of a palpable thrill or audible bruit along some point of the arteriovenous dialysis access beyond the arteriovenous anastomosis).

11.2.8.9 30-day occurrence of Interventions or Hospitalizations

Occurrence of events occurring within 30 days of implantation that require reinterventions (open or endovascular), hospitalizations, or prolongation of existing hospitalization

11.2.8.10 Occurrence of Events:

Occurrence is defined as the overall number of each event listed below that occur in the defines time period.

- Occurrence of reported reduction of blood flow that prevents the ability to cannulate or requires further assessment and/or intervention from baseline to 12 months.
- Occurrence of reported inability to cannulate fistula beginning once the fistula is deemed radiographically and clinically mature to 12 months.
- Occurrence of the development of steal syndrome from baseline to 12 months.
- Occurrence of bleeding requiring surgical intervention (including PRBC transfusion) from baseline to 12 months.
- Occurrence of infiltration requiring procedural intervention from baseline to 12 months.
- Occurrence of hematoma requiring procedural intervention from baseline to 12 months.
- Occurrence of the inability to use the EchoSure component of the system, from baseline to 4 months, due to:
 - Migration of the EchoMark device
 - Early resorption of the EchoMark device as defined as breakdown of the EchoMark shape prior to 4 months from index procedure.
- Occurrence of pain caused by the study devices beginning at baseline to 12 months.
- Occurrence of infection (not limited to infection requiring implant explantation) beginning at baseline to 12 months.

• Occurrence of infection confirmed by either implant explantation or purulent fluid on pathologic assessment during incision and drainage beginning at baseline to 12 months.

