3.5 Preliminary Investigations

Benchtop Performance Data

Purpose

Test Procedure

	╸ ╸╴╸	

ISO 10993 biocompatibility testing was performed on the EchoMark device. Results from the tests indicate that the device is non-toxic, non-sensitizing, non-mutagenic and non-irritating therefore biocompatible for its intended use.

EchoSure Probe

Sonavex has also performed extensive biocompatibility testing on EchoSure Probe. Biocompatibility testing of the EchoSure Probe devices was conducted in accordance with ISO 10993 series standards and EP/USP guidance documents as applicable. Additional guidance for the performance of these tests comes from the U.S. FDA June 2016 Guidance Use of International Standard ISO 10993-1, "Biological evaluation of medical devices - Part 1: Evaluation and testing within a risk management process". All tests were conducted in compliance with applicable requirements in the good laboratory practice (GLP) regulations in 21 CFR 58. The specific studies include:

ISO 10993 biocompatibility testing was performed on the EchoSure Probe. Results from the tests indicate that the device is biocompatible for its intended use.

Summary of Outcomes Compared to Literature

In order to evaluate the longer-term impact on outcomes, maturation rates were also evaluated for the subjects in the studies. A total of 34 fistula patients were followed to the first maturation assessment or longer. A summary of the outcomes for EchoMark patients are included below alongside cited literature for non-EchoMark AV fistula patients.

	Sonavex EchoMark Patients ¹	Sonavex EchoMark (>90-day postop) ²	Woodside 2018 (USRDS Data)	Robbin 2018 (HFM Study)	Chan 2018
Number of Patients/AVFs	34	30	45,087	587	146
% Mature	73.5%	83.3%	64%	72%	72%
% Failed	11.8%	16.7%	36%	28%	28%
% Outcome Not Yet Known*	14.7%	N/A	N/A	N/A	N/A

* A maturation determination has either not yet been determined or not yet communicated to Sonavex. ¹ All patients who underwent a first maturation assessment.

² All patients with a maturation outcome assigned or who are at least 90 days post-surgery. Though the national average time to maturation is over 6 months, out of caution, patients who received their AV fistula procedure more than 90 days ago were assigned as 'failure.'

Note: A total of 7 patients had follow-ups occurring after the study was suspended on January 7. These results were communicated to Sonavex verbally and represent 2 mature AVFs, 1 failed AVF, and 4 'outcome not yet known.'

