The exact binomial method was used for EchoMark patients with 90-day follow-up to estimate the 95% confidence interval for maturation success. Centered around the 83.3% successful maturation rate, the 95% CI is [65.3% - 94.4%]. Thus, the existing sample size appears adequate to demonstrate that maturation success in the EchoMark patient population is in line with recent large AVF cohort studies^{3,4,5,6,7}. Based on the results above, Sonavex has no reason to believe that EchoMark introduces additional risk to AV fistula patients. In fact, given historic average maturation times of 6-9 months it is likely that many of the patients in "outcome not yet known" may become successes, pushing the maturation success to a level higher than other recent large multicenter reports.

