4.2.3 Observational Assessments

The following observational assessments will be performed and/or summarized:

- Comparison of EchoSure and duplex measurements of flow, diameter, and depth. Only duplex images that pass a quality control check by an Independent RVT will be included in the assessment.
- Comparison of EchoSure depth measurements to Independent Reviewer measured depth results.

- Time to radiographic maturation is defined as the number of days from baseline procedure to date of radiographic maturation (date of ultrasound imaging, as adjudicated by the CEC). Radiographic maturation is defined as a fistula with volume flow of 500mL/min and 5mm diameter.
- Time to clinical maturation defined as the number of days from baseline procedure to date of clinical maturation. Clinical maturation is defined as 75% of dialysis sessions with successful 2 needle cannulation for 4 weeks. Date of clinical maturation is defined as first date of the 4-week window when clinical maturation is achieved.
- Radiographic maturation success rate defined as the percentage of subjects that achieve radiographic maturation (as determined by the physician and adjudicated by the CEC) by end of study. Radiographic maturation is defined as a fistula with volume flow of 500mL/min and 5mm diameter.
- Clinical maturation success rate is defined as the percentage of subjects that achieve clinical maturation by end of study. Date of clinical maturation is defined as first date of the 4-week window when clinical maturation is achieved.
- 6-month patency rate as defined by the status (yes/no) of an arteriovenous dialysis access with detectable blood flow through and beyond the anastomosis shown by either an imaging modality or physical examination (presence of a palpable thrill or audible bruit along some point of the arteriovenous dialysis access beyond the arteriovenous anastomosis). ⁸
- 12-month patency rate as defined by the status (yes/no) of an arteriovenous dialysis access with detectable blood flow through and beyond the anastomosis shown by either an imaging modality or physical examination (presence of a palpable thrill or audible bruit along some point of the arteriovenous dialysis access beyond the arteriovenous anastomosis).
- Occurrence of events occurring within 30 days of implantation that require reinterventions (open or endovascular), hospitalizations, or prolongation of existing hospitalization.

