11.2.4 Analysis Samples

The primary and observational analysis samples will include all enrolled subjects with successful EchoMark LP implantation.

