11.2.8 Analysis of Observational Endpoints

Observational endpoints are defined in Section 4.2.

For discrete endpoints, the number and percentage of subjects with success will be summarized. Descriptive statistics for components of each endpoint will also be provided.

For continuous variables (e.g., volume flow, depth, and diameter), results will be summarized with the with the numbers of observations, means, medians, standard deviations, minimums, and maximums. Change from baseline will be included using these same descriptive statistics.

11.2.8.1 Comparison of EchoSure volume flow, diameter and depth to Duplex values:

The degree of correlation between paired EchoSure values and Duplex values that pass the quality checks by an Independent RVT will be analyzed.

The comparison data points are:

- EchoSure vessel depth at EchoMark vs Duplex vessel depth at EchoMark
- EchoSure vessel diameter at EchoMark vs Duplex vessel diameter at EchoMark
- EchoSure volume flow at EchoMark vs Duplex volume flow at cannulation zone (standard of care)

All Duplex volume flow, depth and diameter data points will undergo quality checks performed by an Independent RVT to qualify for inclusion in the comparison analyses. The quality checks will assess if the Duplex data was collected per protocol and meet defined requirements that ensure a uniform technique.

Duplex volume flow data points that do not pass the quality checks will not be included in the analysis. The paired EchoSure flow values for failing Duplex values will also not be included.

Duplex diameter and depth values that do not pass the quality checks will be corrected by an Independent RVT. The corrected Duplex depth and diameter data points will be included in the analysis along with their paired EchoSure values.

All sites and their sonographers will be trained on the Duplex data collection protocol and quality requirements. Each site will be required to submit a set of images for quality checks by an Independent RVT as a part of site qualification.

Degree of correlation between paired EchoSure values and Duplex values (volumetric flow, vessel diameter, vessel depth, etc.) that pass quality checks will undergo the following analyses:

- Pearson Correlations to assess correlation
- Bland Altman testing using percentages will be used to assess for bias and the limits of agreement
- Distribution of correlation percentage between EchoSure and Duplex values

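### Sections 11.2.8.7 and 11.2.8.8 make 6- and 12-month patency conditional on maturation, against the flow-only definition in Section 4.2.3, without stating the denominator or the date of the condition

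*Combined protocol and SAP*

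**What the plan says.** Section 4.2.3 and the synopsis define both patency rates by flow status alone, shown by imaging or by physical examination: "6-month patency rate as defined by the status (yes/no) of an arteriovenous dialysis access with detectable blood flow through and beyond the anastomosis". They attach no maturation condition. Section 11.2.8 points back to that text: "Observational endpoints are defined in Section 4.2".

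The first paragraph of Section 11.2.8.7 nevertheless defines the rate as the "percentage of subjects that have patent access at 6 months if both radiographic and clinical maturation definitions have been met". Section 11.2.8.8 has the parallel wording, "percentage of subjects that have patent access at 12 months if both radiographic and clinical maturation definitions have been met". The second paragraph of each section then returns to flow alone, for example "12-month patency rate as defined by the status (yes/no) of an arteriovenous dialysis access with detectable blood flow through and beyond the anastomosis".

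Four other places bear on the point:

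- **Section 11.2.4** sets the sample: "The primary and observational analysis samples will include all enrolled subjects with successful EchoMark LP implantation".
- **Section 7.8** brings all subjects to the 180-day and 12-month visits. The physical exam there covers bruit and thrill, and a flow/no-flow assessment is adjudicated by the CEC.
- **Sections 11.2.8.5 and 11.2.8.6** count maturation reached by end of study, and Section 5.3 puts study exit at no later than 24 months.
- **Section 3.5** describes slow maturation: "Though the national average time to maturation is over 6 months" and "given historic average maturation times of 6-9 months".

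**The concern.** An analyst who follows Sections 11.2.8.7 and 11.2.8.8 as written does not compute the endpoint in Section 4.2.3. The conditional clause can also be applied in two ways. It can restrict the denominator to matured fistulas, or it can add maturation to the success criterion while all implanted subjects stay in the denominator. Section 11.2.4 names the sample but does not choose between these, and Section 11.2.10 deals only with missing values.

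The date is open as well. A fistula that is patent at month 6 and matures at month 8 meets the condition if maturation counts up to end of study, and fails it if maturation must precede the visit. The maturation times cited in Section 3.5 make this a realistic case, mainly for the 6-month rate.

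Two careful analysts could therefore report different percentages from one dataset under the same endpoint name. With at most 20 subjects, each subject moves an all-implanted rate by 5 points.

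**Working it through.** The plan states no expected patency rate, so there is no patency figure to reproduce. The maturation rates in Section 3.5 serve only to set plausible counts. The sponsor's own >90-day figure does reproduce: 25/30 = 83.3%, with an exact 95% interval of 65.3% to 94.4%, as printed.

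**Inputs**

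- N = 20 implanted (Section 11.1, the planned maximum).
- Maturation rates in the Section 3.5 table: 64%, 72%, 73.5% and 83.3%. Times 20 these give 12.8, 14.4, 14.7 and 16.7, so m = 13, 14, 15 and 17 matured. **Assumption:** these rates stand in for joint radiographic and clinical maturation; the documents do not show that they match it.
- **Assumption:** l = 0 or 1 matured fistula is not patent.
- f = number of non-matured fistulas with flow, anywhere from 0 to 20 − m.

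**Formulas**

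- Flow only (Section 4.2.3): A = (m − l + f)/20
- Condition restricts the denominator: B = (m − l)/m
- Condition is part of success: C = (m − l)/20
- Difference on the same data: B − C = (m − l)(20 − m)/(20m)

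**Results**

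| m | l | B | C | B − C (points) | A, from f = 0 to f = 20 − m |
|---|---|---|---|---|---|
| 13 | 0 | 13/13 = 100.0% | 13/20 = 65.0% | 35.0 | 65% to 100% |
| 13 | 1 | 12/13 = 92.3% | 12/20 = 60.0% | 32.3 | 60% to 95% |
| 14 | 0 | 14/14 = 100.0% | 14/20 = 70.0% | 30.0 | 70% to 100% |
| 14 | 1 | 13/14 = 92.9% | 13/20 = 65.0% | 27.9 | 65% to 95% |
| 15 | 0 | 15/15 = 100.0% | 15/20 = 75.0% | 25.0 | 75% to 100% |
| 15 | 1 | 14/15 = 93.3% | 14/20 = 70.0% | 23.3 | 70% to 95% |
| 17 | 0 | 17/17 = 100.0% | 17/20 = 85.0% | 15.0 | 85% to 100% |
| 17 | 1 | 16/17 = 94.1% | 16/20 = 80.0% | 14.1 | 80% to 95% |

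B and C differ by 15.0 to 35.0 points when every matured fistula is patent, and by 14.1 to 32.3 points when one is not.

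**Against the Section 4.2.3 endpoint.** C is never above A, and equals it only when no non-matured fistula has flow. B can lie on either side of A. With m = 13 and l = 1, B = 92.3% while A runs from 60% to 95%. In a middle case (m = 14, l = 1, f = 3), A = 16/20 = 80.0%, so B is 12.9 points too high and C is 15.0 points too low.

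**Does the denominator of the flow-only rate matter too?** Take the same middle case, with 16 of 20 patent. Suppose 3 of the 4 fistulas without flow were abandoned and have no flow record. A rate among assessed subjects only would be 16/17 = 94.1%, against 16/20 = 80.0%. Deleting the clause is therefore not enough; the handling of unassessed subjects must also be shown.

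**The case against.** The strongest reply is that the clause is deliberate. It appears in identical form in two sections, and another endpoint in Section 4.2.3 (inability to cannulate) also starts only at radiographic and clinical maturity. The first paragraph would then define the rate and the second would merely define patent access. A matured-access rate may indeed be wanted, and the documents do not prove otherwise. But that endpoint shows that Section 4.2.3 states a maturity condition where it intends one. It states none for patency, and Section 11.2.8 names Section 4.2 as the source. Even on the deliberate reading, the denominator and the date remain unstated.

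It is also fair to say that little hangs on this. Section 11.1 sets no hypothesis to test, maturation and fistula failure are reported separately, and Section 11.2.1 promises subject listings. That stands and limits the weight of the point. Listings let a reader recalculate; they do not say which percentage is the endpoint.

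A reader might infer more than the documents support:

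- **Gaps of 45 or 58 points.** These need only 10 or 6 of 20 fistulas matured (50% or 30%), below every rate in the Section 3.5 table. The average times of over 6 months or 6-9 months give no proportion matured at the visit.
- **Conditioning always flatters the device.** It does not: C is never above the flow-only rate, and B can fall below it.
- **No patency data for abandoned fistulas.** Section 7.11 lists no flow/no-flow item, but it keeps these subjects on the 180-day and 12-month visits, and Section 7.8 applies its assessment to all subjects there.
- **The 4-week cannulation window leaves the maturation date undefined.** Sections 4.2.3 and 11.2.8.4 date clinical maturation to the first day of the window. The larger gap is that the only stated limit on maturation is end of study.

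**Conclusion.** The point holds. Sections 11.2.8.7 and 11.2.8.8 conflict with Section 4.2.3, and with their own second paragraphs, on whether patency requires maturation. They leave open both the denominator and the date of the condition. In the illustration the two readings differ by about 14 to 35 points. That range rests on 20 implanted subjects, 13 to 17 matured, and none or one of these not patent. The maturation counts are assumed, because the documents give no joint maturation rate at either visit.

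The consequence is confined to two descriptive observational rates. No primary endpoint, hypothesis test or sample size is affected. It should be corrected before 6-month patency is summarised, but it does not threaten the study.

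**What to change.** 1. In Sections 11.2.8.7 and 11.2.8.8, delete the clause that makes patency conditional on maturation, so that both rates match Section 4.2.3.
2. Report each rate for the Section 11.2.4 sample from the Section 7.8 flow/no-flow assessment. State that this includes subjects with abandoned fistulas who attend these visits under Section 7.11.
3. Give the number without an assessment and the reasons (for example exit after explantation under Section 7.12, withdrawal or death).
4. Add one line showing the rate with unassessed abandoned fistulas counted as not patent, so that likely failures do not silently leave the denominator.
5. If patency among matured fistulas is wanted, report it as a separate, labelled rate with its denominator and an explicit date by which maturation must be reached.

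The cost is one clause removed in two places, a sentence or two on the denominator, and one extra reported line. No new visits or procedures are needed. The downside is that the headline rate may be less favourable than a rate among matured fistulas only.

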11. STATISTICAL ANALYSIS

11.1. Sample Size Considerations

This is a feasibility study and accordingly there is not a pre-specified null hypothesis to be tested against for the study endpoints. Data collected from this study will provide preliminary device safety and effectiveness data for the use of the EchoMark/EchoSure System in patients receiving arteriovenous fistulae for hemodialysis access. Descriptive statistics will be reported for the study data. Inferential statistical analysis will be conducted in an exploratory manner. The sample size for this study is planned to be up to 20 subjects at up to 4 investigational sites, with data points collected at multiple timepoints for each subject.

Statistical methods for the study are outlined below.

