11.2. Data Analysis Plan

11.2.1 General Principles

All statistical analyses will be performed using Statistical Analysis System (SAS) for Windows (version 9.4, SAS Institute Inc. Cary, NC), STATA (version 16, StataCorp, College Station, TX) or other widely accepted statistical or graphical software. All statistical analysis will be conducted by an independent statistician.

Descriptive statistics will be used to present the data and to summarize results. Discrete variables will be presented using frequency distributions and cross tabulations. Continuous variables will be summarized by presenting the number of observations (N), mean, standard deviation, median, minimum, and maximum values. In general, data for all study subjects combined will be presented. The primary analysis for all baseline characteristics and study outcomes will include all available data for all enrolled subjects. Individual data will be presented in subject listings.

Summaries of the following endpoints present the number and percentage of unique subjects within an event, unless specified otherwise: protocol deviations; subject status; adverse events. Thus, multiple occurrences of the same event are counted only once per subject, unless specified otherwise.

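### Section 11.2.8.10 reports each listed event as a total count, which does not give the proportion of subjects affected; add subjects with at least one event over a named denominator

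*Combined protocol and SAP*

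**What the plan says.** Section 11.2.8.10 (Occurrence of Events) opens with its definition: "Occurrence is defined as the overall number of each event listed below that occur in the defines time period". Ten items follow. Eight run from baseline to 12 months. The item on being unable to use EchoSure stops at 4 months. One has a start date that differs by subject: "Occurrence of reported inability to cannulate fistula beginning once the fistula is deemed radiographically and clinically mature to 12 months".

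Three other sections bear on how these items are summarised:

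- Section 11.2.1 says that summaries of protocol deviations, subject status and adverse events "present the number and percentage of unique subjects within an event, unless specified otherwise", and that "multiple occurrences of the same event are counted only once per subject, unless specified otherwise".
- Section 11.2.8 says of the observational endpoints generally: "For discrete endpoints, the number and percentage of subjects with success will be summarized". It has no exception clause.
- Section 11.2.4 supplies a possible denominator: "The primary and observational analysis samples will include all enrolled subjects with successful EchoMark LP implantation". Section 11.2.8.10 does not refer to it.

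Section 11.2.8.11, directly after the event list, summarises the 12-month composite as a proportion of subjects.

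**The concern.** A total of events answers how many episodes occurred. For harms of an implant the first question is how many subjects were affected, and out of how many. The two answers differ whenever one subject can contribute more than once. The protocol expects that: Section 9.5 asks for the onset and duration of every episode of an intermittent adverse event. Pain, infection, reduced flow and inability to cannulate are natural candidates.

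Exposure also differs between subjects. Under Section 7.12 a subject whose marker is explanted leaves once the event has resolved. Under Section 10.2 a subject who withdraws after receiving the device is not replaced. A subject whose fistula never matures is never at risk for the cannulation item. Section 11.2.10 has no rule for incomplete follow-up beyond not imputing.

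What is at stake is how the itemised safety results can be read. Infections would be a count in 11.2.8.10, while device-related infection enters a per-subject composite in 11.2.8.11, so the two tables would use different units. Section 4.2.1 plans a summary and a pivotal request after the 90-day window closes. If these events are summarised then, follow-up will be unequal across subjects and a bare count will be hardest to interpret.

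**Working it through.** **Inputs.** N = 20 is the planned maximum in Section 11.1 ("The sample size for this study is planned to be up to 20 subjects"). The reported count of 4 events is an assumption for illustration; the plan gives no expected count.

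**Formula.** Exact (Clopper-Pearson) 95% limits for x subjects out of n are the 2.5% quantile of Beta(x, n − x + 1) and the 97.5% quantile of Beta(x + 1, n − x).

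**Check against the plan's own interval.** Section 3.5 reports 83.3% of 30 earlier patients mature, with an exact interval of 65.3% to 94.4%. Here x = 0.833 × 30 = 25, and the formula with 25/30 returns 65.3% to 94.4%. It agrees.

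**What a reported count of 4 can mean with N = 20**

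| Subjects affected | Events per affected subject, for example | Proportion | Exact 95% CI |
|---|---|---|---|
| 1 | 4 | 5.0% | 0.1% to 24.9% |
| 2 | 2 and 2 | 10.0% | 1.2% to 31.7% |
| 3 | 2, 1 and 1 | 15.0% | 3.2% to 37.9% |
| 4 | 1 each | 20.0% | 5.7% to 43.7% |

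The same summary line fits a fourfold range of proportions (20.0 / 5.0 = 4). With zero events the count and the subject number agree, but the precision is still missing: for 0/20 the upper limit is 1 − 0.025^(1/20) = 16.8%.

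**Inability to cannulate.** Suppose only 10 of the 20 subjects meet both maturation definitions (an assumption). Four affected subjects are then 4/10 = 40.0% (12.2% to 73.8%) of those at risk, against 4/20 = 20.0% of all implanted subjects. Time at risk differs too. Taking 12 months as 365 days, maturity at day 60 leaves 365 − 60 = 305 days and maturity at day 180 leaves 365 − 180 = 185 days.

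**Why follow-up time belongs beside the count.** Four events are 4/20 = 0.20 per person-year over 20 person-years (exact Poisson 95% CI 0.05 to 0.51), but 4/10 = 0.40 over 10 person-years (0.11 to 1.02). Both person-year totals are assumptions, and the intervals treat events as independent, which repeats within a subject may not be.

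**The case against.** The strongest reply is that the sponsor has chosen a count and was free to do so. A reader might infer that 11.2.8.10 contradicts 11.2.1. The documents do not support that: both 11.2.1 sentences allow exceptions, and 11.2.8.10 is one. A reader might also see a flat conflict with 11.2.8. That rule speaks of subjects with success, which suits maturation and patency but not harms, so it is a poor fit rather than a clear contradiction.

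Per-subject information is also planned elsewhere. Listed items that are recorded as adverse events may still fall under the unique-subject summary in 11.2.1. Individual listings are promised, and with about 20 subjects a reader could rebuild the subject counts from them. This stands in part. The ambiguity lies in the summary, not in the data, but rebuilding from listings leaves the denominator and the at-risk set to be chosen after the results are known.

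A reader might go further and suppose that one displaced marker could be counted at every scan and visit. Nothing in the plan counts per scan. Section 12.7 has the Clinical Events Committee confirm events and see that they are counted accurately, and Section 7.10 calls for an adverse event form and suspends EchoSure scans once the fistula is outside the marker.

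Finally, the missing intervals are not peculiar to this section. Section 11.1 makes the whole study descriptive, with any inference exploratory. That is fair. An exact interval needs no hypothesis, though, and the protocol used one for its earlier cohort.

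**Conclusion.** The point holds as a matter of reporting. The definition in 11.2.8.10 yields a number that cannot be read as the proportion of subjects affected for events that can recur, and it gives no at-risk set for the cannulation item. In the illustration, one reported count fits 5.0% to 20.0% of subjects, with exact limits running from 0.1% to 43.7% across those readings. This rests on N = 20, an assumed count of 4 and recurrence within subjects. It also leaves out roll-in subjects, who are additional to the 20 and whom 11.2.4 does not mention. For an item that cannot recur and has a common start date, the count equals the number of subjects and only the denominator and interval are missing.

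The case for requiring Kaplan-Meier or competing-risk estimates is weak. Ten items, most of them likely to be sparse in 20 subjects, would gain little, and showing follow-up time makes early exits visible. The effect is confined to observational safety summaries.

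**What to change.** Reword 11.2.8.10 as follows:

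1. The main summary for each listed event is the number and percentage of subjects with at least one such event in the item's stated window (12 months, or 4 months for the EchoSure-use item), with an exact 95% CI.
2. The denominator is the 11.2.4 analysis sample. For inability to cannulate it is the subjects who have met both the radiographic and the clinical maturation definitions, with the window starting at that point.
3. A second line gives the total number of events and the follow-up time at risk, so that repeats and early exits can be seen.

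State that this is how the 11.2.8 rule for discrete endpoints applies to harms. With the cannulation item marked as having its own denominator, the other 12-month items then share a per-subject unit with 11.2.8.11, although definitions still differ (any infection against device-related infection).

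The cost is about one paragraph of analysis text and a few extra table columns. No new data are needed: time of onset is already collected under Section 9.5, and the reason for leaving the study under Section 10.2.
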